9.3.3 IBS DIAGNOSIS AND SEVERITY DEFINITION

The target indication of linaclotide is the treatment of moderate-to-severe IBS-C in adults. There are several Read, SNOMED, ICD-9, or ICD-10 codes related to IBS.

GP testimonies gathered during our pilot study, suggests that patients with IBS are frequently assigned IBS codes after other diagnosis have been ruled out and not necessarily during initial consultations, consistent with published research (Harkness EF et al., 2013a and b). Instead, codes of abdominal pain and other abdominal symptoms, suggestive of IBS, and codes of abdominal examinations were mentioned as part of the codes used for these patients. Sometimes, confirmed diagnosis of IBS might not be coded as such and might only remain in the patient's record's notes.

In order to identify potential cases of IBS-C patients using codes, specific IBS-C codes and a combination of an IBS code with a code for constipation will be used. A combination of a code for abdominal pain and at least two abdominal unspecific codes, in addition to a code for constipation will also be used to identify potential cases of IBS-C. [Table 4](#), [Table 5](#) and [Table 6](#) in Annex 3 include a broad list of Read codes, ICD-10, and ICD-9 codes for the identification of patients with IBS with different levels of specificity, as well as codes for constipation to be used in combination.

There are no Read, ICD-9, or ICD-10 codes to indicate the severity of IBS. The most studied and most commonly used tools for measuring IBS severity involve quality-of-life and patient-reported symptom metrics that are not routinely recorded in the computerised databases selected for this study.

9.3.4 VALIDATION OF THE DIAGNOSIS AND SAFETY ENDPOINTS

Information on IBS-C is not well-captured by standard diagnosis codes. SCD is also not coded as such in the databases. Therefore, IBS-C and SCD will be validated by the physicians treating the patients selected as cases or as controls. This will require additional primary data collection from GPs that is possible in the UK with the use of CPRD.

The process in the UK would consist of asking cases' attending GPs to confirm the type of IBS. All cases (patients with IBS-C experiencing SCD) will be characterised in further detail through contact with their PCPs. A questionnaire will be mailed to the GP with whom each identified subject is registered to validate both diagnoses (IBS and SCD [if applicable]; please refer to [Annex 3](#)).

The feasibility of using this questionnaire to collect validation information about cases was evaluated through a pilot study with a small number of physicians in the UK. This UK pilot study targeted a group of 25 PCPs to test the questionnaire and contribute to its development. The section, *Pilot Study Summary Report*, in Annex 3 reports on the pilot study conduct. This pilot study included additional questions to PCPs about preferred codes or code combinations used to record diagnoses of patients with IBS-C.

Although it was originally planned for the validation study to also be undertaken in Spain using GP questionnaires, since 2018, SIDIAP no longer allows the possibility to contact physicians for extracting extended additional information on the patient through long- questionnaires. However, there is the possibility of a text review of the primary care records. This text review can be used to validate cases of interest, conducted by IDIAP's clinical researchers. For this study, it is recommended by the data custodians that a review of free-text in the patient's medical records is conducted to improve the validity of the actual study, in place of the previously planned validation strategy using questionnaires to GPs. This free-text review is made after an anonymisation process of the clinical records and a natural language processing of the text.

We will validate our outcome identification algorithm by calculating the positive predictive value and the negative predictive value in both countries.

9.4 DATA SOURCES

In the UK, the proposed data source is the CPRD (both CPRD GOLD and CPRD Aurum). For Sweden and Spain, the proposed data sources are the Swedish NPR linked to the PDR and the SIDIAP, respectively.

A summary of potential data sources that were evaluated for use in the study can be found in the *Database Feasibility Assessment* section in [Annex 3](#).

9.5 STUDY SIZE

If we assume a combined population in the UK, Sweden, and Spain of approximately 120 million people (Eurostat, 2014), a prevalence of IBS recorded in primary care of 3.5% (Harkness et al., 2013) and roughly one-third of those corresponding to IBS-C (Tillisch et al., 2005), then the three proposed databases could be expected to include around 216,000 active IBS-C patients. By December 2016, it was estimated that approximately 9,665 patients would have been exposed to linaclotide in the three target databases, for a combined exposure of more than 4,572 patient-years, with the UK contributing approximately 28% of patients, Spain 25%, and Sweden 47%. These estimated number of patients exposed to linalcotide is now expected to be reached by end of December 2017, so the data collection period has been extended accordingly.

Linaclotide clinical trial results (12 and 26 weeks in length) suggest that about 3% of IBS-C patients exposed to placebo and 19.6% of IBS-C patients exposed to linaclotide will experience diarrhoea over those periods, predominantly within the first weeks of initiating therapy. Among them, 4% in the placebo group and 10.1% in the linaclotide-exposed group will experience severe diarrhoea. Therefore, severe diarrhoea was experienced by 0.13% of all IBS-C patients exposed to placebo and by 1.99% of IBS-C patients exposed to linaclotide (Chey et al., 2012; Rao et al., 2012). Other treatments for patients with IBS-C are also associated with diarrhoea, usually of mild severity (Wood, 2012). Information sent to healthcare professionals by the manufacturer of a drug sometimes prescribed for IBS-C patients in the United States (US) warned of very serious diarrhoea complicated with hypovolaemia, hypotension, and syncope that required admission to the hospital and intravenous therapy in approximately one in 2,500 patients (or 0.04%) (Wooltorton, 2004).

9.5.1 COHORT SIZE

The linaclotide PASS is a case-control study nested in a cohort of patients with IBS-C. The information of main interest from the databases (refer to Section 9.3.4. *Validation of the Diagnosis and Safety Endpoints*) will be validated for cases and controls through primary data collection from GPs. If the validation results are satisfactory (positive predictive value of EMRs $\geq 95\%$ and negative predictive value $\geq 99\%$), then information from the whole cohort would be used to estimate the incidence of diarrhoea and the incidence of SCD in the cohort of IBS-C patients and the relative risks of SCD and the exposures of interest (mainly prescriptions of linaclotide). Otherwise, only ORs of SCD and the same exposures of interest will be estimated using data from cases and controls.

Table 2 illustrates a range of sample sizes that are required to have 80% power to detect a certain OR for SCD, comparing patients with IBS-C and a certain risk factor to patients with IBS-C and no risk factor, assuming that patients with IBS-C and no risk factor experience SCD with a variety of incidences.

A cohort of patients with IBS-C, and assuming that 5% of subjects in that cohort will have the risk factor of interest, would require a total of approximately 200,000 patients (including 10,000 exposed to the risk factor of interest) with the necessary data for the analysis to have at least 80% power to detect the combination of increased OR (or larger ORs) for the incidence of SCD (or higher incidence); these are in bold in Table 2.

To detect an OR of ≥ 1.5 with 80% power at a 1.0% outcome incidence among unexposed patients, a minimum of 85,416 patients with IBS-C is required in the cohort. For an OR of ≥ 2 , the required sample size is 25,022 patients. At a 0.5% outcome incidence among unexposed patients, the required sample size increases to 169,442 patients for detecting an OR of ≥ 1.5 , and 49,501 patients for detecting an OR of ≥ 2 , with 80% power.

Table 2. Sample Sizes of IBS-C Patients Exposed or Non-Exposed (Total Sample Size) to Risk Factors of Severe Complications of Diarrhoea (SCD) Required to Identify Increased ORs for SCD*

Outcome incidence in unexposed	OR = 1.5	OR = 2	OR = 3	OR = 4	OR = 6	OR = 8
0.01%	8,404,791	2,448,728	776,301	414,607	197,410	124,546
0.02%	4,203,079	1,224,630	388,274	207,387	98,760	62,318
0.05%	1,682,052	490,173	155,457	83,055	39,572	24,981
0.1%	841,711	245,354	77,852	41,612	19,841	12,534
0.2%	421,541	122,944	39,049	20,890	9,977	6,312
0.5%	169,442	49,501	15,768	8,458	4,059	2,579
1.0%	85,416	25,022	8,009	4,315	2,087	1,335

* Significance level is two sided $\alpha = 0.05$ and power is $1 - \beta = 80\%$, 20:1 number of unexposed to exposed patients with IBS-C (equivalent to 5% exposure to risk factor), according to Fleiss (2003), Statistical Methods for Rates and Proportions, (with continuity correction).

Abbreviations: OR = odds ratio

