Using the latest available information, the sample size across the three countries is approximately 329,000 patients with IBS-C or potential IBS-C, with an exposure to linaclotide rate ranging from 1% to 4%. If the results of the validation of cases are satisfactory with positive predictive value of SCD algorithms in the UK and Spain $\geq 95\%$, information from the whole cohort will be used to estimate risk of developing SCD across the groups of patients with or without linaclotide exposure, under a cohort study design. If the positive predictive values are $< 95\%$, a case-control analysis will be performed. Assuming the percentage of patients exposed to linaclotide among controls is around 1%, a minimum of 401 case-control pairs would be required to detect an $OR \geq 4$ and 745 possible case-control pairs to detect an $OR \geq 3$ with 80% power, under a matched case-control study design. Within the total IBS-C cohort, it is expected to accrue approximately 11,800 algorithm-identified, potential SCD cases. The final number of case-control pairs to be included in the analyses will depend on the performance of SCD algorithms and case validation results and is expected to be sufficient to detect an $OR \geq 3$ at 80% power, given the number of potential SCD cases identified by the algorithms.

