Initially, we proposed conducting the study with data collected up to December 2016, but based on the patients counts accrued by December 2016, the data collection period was extended. In the current version of the protocol, the data collection period has been extended to the date of the most recent data available in HES and CPRD at the time of data access for the UK only. As CPRD including Aurum data is about two times larger than the last data extraction, we expect more than 200,000 patients with IBS-C in CPRD. Among them, based on market uptake forecasts, we would also expect having around 2,000 patients exposed to linaclotide by that date (as potential risk factor of interest, or approximately 1% of patients with IBS-C).

If SCD occurs with a frequency of 0.05% among patients with IBS-C (cases) and we select one or more controls per case, then 94 case-controls sets would allow the detection of OR = 4 (or larger), with 80% power for a risk factor present in 5% of controls (approximately the expected proportion of patients with IBS-C exposed to linaclotide).

If we assume that SCD occurs with a frequency of 0.08%, then around 168 case-control sets would allow the detection of OR = 3 or larger, with 80% power for a risk factor present in 5% of controls (in bold in Table 3).

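### The cohort sizes in 9.5.1 use about 5% exposure, outdated for linaclotide at the protocol's own 1–4%, so the stated 80% power does not hold for the main exposure

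*Protocol*

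**What the plan says.** Section 9.5.1 names linaclotide prescription as the main exposure of the cohort analysis. It introduces its illustration by "assuming that 5% of subjects in that cohort will have the risk factor of interest". The next paragraph gives four total cohort sizes for 80% power: 85,416 (OR 1.5) and 25,022 (OR 2) at 1.0% incidence in the unexposed, and 169,442 and 49,501 at 0.5%. For the first, "a minimum of 85,416 patients with IBS-C is required in the cohort". All four are cells of Table 2, whose footnote gives the ratio as "20:1 number of unexposed to exposed patients with IBS-C (equivalent to 5% exposure to risk factor") and the method as the Fleiss formula with continuity correction.

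Elsewhere the protocol gives lower exposure:

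- Section 4.8, on the latest information, reports about 329,000 patients "with an exposure to linaclotide rate ranging from 1% to 4"%. It sizes the case-control analysis at about 1% exposure among controls (401 pairs for OR 4, 745 for OR 3).
- Section 9.5.2 expects around 2,000 linaclotide users among more than 200,000 CPRD patients, "approximately 1% of patients with IBS-C". Its next paragraph still treats 5% as roughly the expected proportion exposed to linaclotide.

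**The concern.** The case-control size was brought up to date for low uptake and the cohort size was not. Five per cent lies outside the range that the protocol now reports. Table 3 runs from 0.1% to 9% exposure, but Table 2 offers a single exposure level, so a reader cannot look up the cohort size that applies to linaclotide.

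The amendment log records that text on cohort sample sizes was added in version 13.3 at PRAC's request. As printed, all four minima are well below 329,000, which suggests ample power for an OR of 1.5 whatever the incidence. If exposure is nearer 1%, that impression is right only above a certain incidence, and the section does not say so.

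**Working it through.** **Inputs.** Two-sided alpha 0.05, 80% power, continuity correction and 20 unexposed per exposed (Table 2 footnote). Incidence in the unexposed p0 = 1.0% or 0.5%, and OR 1.5 or 2 (9.5.1). Exposure 1–4%, 329,000 patients and about 11,800 potential cases (4.8).

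**Formula.** With r unexposed per exposed:

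- p1 = OR·p0 / (1 − p0 + OR·p0); d = p1 − p0; p̄ = (p1 + r·p0)/(1 + r)
- m = [1.96·√((r+1)·p̄(1−p̄)) + 0.8416·√(r·p1(1−p1) + p0(1−p0))]² / (r·d²)
- with continuity correction, m_c = (m/4)·[1 + √(1 + 2(r+1)/(m·r·d))]²
- total N = (1 + r)·m_c

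**Reproducing the plan.** For p0 = 0.01 and OR 1.5, p1 = 0.014925 and d = 0.004925. At r = 20, m = 3,857.0 and m_c = 4,067.4, so N = 21 × 4,067.4 = 85,415 (printed 85,416). The other three come to 25,021, 169,443 and 49,500. Table 2 is therefore right for its own ratio, which strictly is 1/21 = 4.76% exposed.

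**Changing only the exposure.** Put r = (1 − e)/e for exposure e. At e = 1%, r = 99, m = 3,682.0 and m_c = 3,884.4, so N = 100 × 3,884.4 = 388,440.

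| Incidence, OR | Printed | Needed at 1% | Needed at 2% | Needed at 4% |
|---|---|---|---|---|
| 1.0%, 1.5 | 85,416 | 388,440 | 196,586 | 100,730 |
| 1.0%, 2 | 25,022 | 113,018 | 57,302 | 29,467 |
| 0.5%, 1.5 | 169,442 | 770,503 | 389,953 | 199,821 |
| 0.5%, 2 | 49,501 | 223,546 | 113,348 | 58,295 |

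The needed sizes are about 4.5 times the printed ones at 1% exposure and about 1.18 times at 4%.

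**Power of the printed sizes** (same formula solved for power): 28–30% at 1% exposure, 48–49% at 2%, 63–64% at 3% and 74% at 4%.

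**What the 329,000 patients can detect at 1% exposure:**

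| Incidence in unexposed | Power for OR 1.5 | Smallest OR with 80% power |
|---|---|---|
| 0.5% | 47% | 1.80 |
| 1.0% | 74% | 1.55 |
| 3.4% | about 99% | 1.29 |

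Setting N = 329,000 for OR 1.5 gives a break-even incidence of about 1.2%. For OR 2, power is at least 91% at both incidences that the protocol uses.

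**Where 3.4% comes from.** 11,800 × 0.95 = 11,210 cases, and 11,210 / 329,000 = 3.4%. This takes the lowest PPV at which the cohort analysis is run.

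**The case against.** Several points on the other side are sound.

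- **The assumption is disclosed.** The 5% is stated in the paragraph before the four figures and again in the Table 2 footnote. A reader might infer a calculation error or a hidden assumption; the documents support neither.
- **The printed sizes fit.** A reader might also infer that the printed minima exceed the available cohort. All four are below 329,000. Only the sizes recomputed for OR 1.5 exceed it: both of them at 1% exposure, and the one for 0.5% incidence at 2%. At 4% all four recomputed sizes fit.
- **The cohort analysis is conditional.** The Cox model is run only if PPV is at least 95% and NPV at least 99% (9.7.2.2). The expected case count then implies an incidence near 3.4%, where OR 1.5 is well covered even at 1% exposure. The stronger reading, that a null hazard ratio would be falsely reassuring because the cohort is underpowered, is therefore not supported in general. It would apply only to an OR near 1.5 with low exposure and a validated incidence below about 1.2%.
- **The certain design already uses 1%.** The nested case-control analysis is sized at 1% exposure in 4.8, and section 7 calls the study descriptive with no a priori hypothesis.
- **Table 2 is generic.** It covers risk factors in general, and 5% may suit others.

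These points reduce the consequence. They do not make 80% power true for linaclotide at the stated incidences, and they do not remove the contradiction within 9.5.2.

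**Conclusion.** The defect is a superseded planning input. For linaclotide at the exposure that the protocol now reports, the four sizes in 9.5.1 do not give 80% power at their own stated incidences; they give between 28% and 74%. Sections 9.5.1 and 9.5.2 contradict 4.8 on exposure, and 9.5.2 contradicts itself.

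Whether the study falls short depends on incidence. With 329,000 patients and 1% exposed, there is a shortfall for OR 1.5 below about 1.2% incidence in the unexposed, and none at about 3.4%. The 3.4% rests on three assumptions: about 11,800 algorithm-identified cases, a PPV of 95% that also holds in Sweden (where there is no validation study), and an overall incidence close to that in the unexposed. The comparison also uses the protocol's two-proportion approximation rather than the Cox model itself.

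This should be corrected because it concerns the power statement for the main exposure, but it changes no planned analysis or estimate.

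**What to change.** 1. Recompute Table 2 and the four figures in 9.5.1 at 1%, 2% and 4% exposure. The 5% column may stay if it is labelled as applying to other risk factors.
2. State the assumed exposure beside each cohort size.
3. Reconcile the 5% statements in 9.5.1, the Table 2 footnote and 9.5.2 with the 1–4% in 4.8.
4. Give the smallest OR detectable with 80% power for the 329,000 patients, across incidences that include the one implied by the expected case count. At 1% exposure these are about 1.80 at 0.5%, 1.55 at 1.0% and 1.29 at 3.4%.

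The cost is a change to text and one table. No data collection, design or analysis changes. The four headline sizes become less favourable, while the statement for the available cohort stays favourable at the incidence that the protocol's case count implies.

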9.5.2 NESTED CASE CONTROL SIZE

Table 3 illustrates a range of sample sizes required to have 80% power to detect a certain OR for those patients exposed or unexposed to a certain risk factor for SCD from a matched case-control study, assuming a range of proportions for exposure of the controls to the risk factor of interest.

A case-control study (Table 3) of SCD cases nested in a cohort of patients with IBS-C (like the one previously mentioned with 200,000 subjects) would require, for example, a total of 94 case-control pairs (equivalent to an incidence of SCD = 0.05%) with the necessary data for the analysis to have at least 80% power to detect an OR = 4 (or larger), associating SCD with a risk factor present in 5% of controls (in bold and grey background in Table 3).

Table 3. Sample Sizes (Case-Control Pairs) of Patients with IBS-C and Severe Complications of Diarrhoea (SCD) to Identify Increased Case-Control OR (Rate Ratio Estimate) for Risk Factors of Interest*

Percentage exposed among controls	OR=1.5	OR=2	OR=3	OR=4	OR=6	OR=8
0.1%	77656	22791	7252	3868	1831	1147
0.5%	15625	4595	1468	786	375	237
1.0%	7872	2321	745	401	193	123
2.0%	3996	1184	384	209	103	67
3.0%	2705	806	264	145	72	48
4.0%	2060	616	204	113	57	38
5.0%	1674	503	168	94	48	33
6.0%	1417	428	144	81	42	29
7.0%	1233	374	127	72	38	27
8.0%	1096	334	114	65	35	25
9.0%	990	303	105	60	33	23

* Significance level is two sided α 0.05 and power is $1 - \beta$ 80%, 1:1 number of cases (IBS C patients with severe complications of diarrhoea) to number of controls (IBS C patients without severe complications of diarrhoea) matched by number of years of active history in the CPRD (± 1 years), IBS C prevalent or incident status, and region. A higher number of matched controls per case would increase statistical efficiency (Pang D, 1999).

Abbreviations: OR odds ratio

Initially, we proposed conducting the study with data collected up to December 2016, but based on the patients counts accrued by December 2016, the data collection period was extended. In the current version of the protocol, the data collection period has been extended to the date of the most recent data available in HES and CPRD at the time of data access for the UK only. As CPRD including Aurum data is about two times larger than the last data extraction, we expect more than 200,000 patients with IBS-C in CPRD. Among them, based on market uptake forecasts, we would also expect having around 2,000 patients exposed to linaclotide by that date (as potential risk factor of interest, or approximately 1% of patients with IBS-C).

If SCD occurs with a frequency of 0.05% among patients with IBS-C (cases) and we select one or more controls per case, then 94 case-controls sets would allow the detection of OR = 4 (or larger), with 80% power for a risk factor present in 5% of controls (approximately the expected proportion of patients with IBS-C exposed to linaclotide).

If we assume that SCD occurs with a frequency of 0.08%, then around 168 case-control sets would allow the detection of OR = 3 or larger, with 80% power for a risk factor present in 5% of controls (in bold in Table 3).

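### Section 9.5.2 still sizes the linaclotide comparison at 5% exposure although it now expects about 1%, so 94 and 168 sets do not give the stated 80% power

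*Protocol*

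**What the plan says.** Three places in the protocol give the share of IBS-C patients exposed to linaclotide.

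- Section 9.5.2, for CPRD after the addition of Aurum: around 2,000 users among more than 200,000 patients, described "as potential risk factor of interest, or approximately 1% of patients with IBS-C".
- Section 9.5.2, next paragraph: "then 94 case-controls sets would allow the detection of OR = 4 (or larger), with 80% power", and this is "for a risk factor present in 5% of controls (approximately the expected proportion of patients with IBS-C exposed to linaclotide". The paragraph after it gives 168 sets for OR 3, also at 5%.
- Section 4.8: about 329,000 patients across the three countries, "with an exposure to linaclotide rate ranging from 1% to 4" percent. It then assumes around 1% among controls and gives 401 pairs for OR 4 and 745 for OR 3. It adds that "it is expected to accrue approximately 11,800 algorithm-identified, potential SCD cases", and that the confirmed yield should suffice for OR 3.

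Section 9.5.1 sizes the cohort at 5% exposure. Table 2 uses 20 unexposed per exposed patient, and the text says that for OR 1.5 at 1.0% incidence "a minimum of 85,416 patients with IBS-C is required in the cohort". The corresponding figures are 25,022 for OR 2 at 1.0% incidence, and 169,442 and 49,501 for OR 1.5 and OR 2 at 0.5% incidence.

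**The concern.** No current estimate in the protocol reaches 5%. That figure matches the superseded forecast in section 4.8, 9,665 users in a cohort of at least 200,000 (9,665/200,000 = 4.8%). The exposure estimate was revised in 4.8 and in one paragraph of 9.5.2, but the worked examples that depend on it were not.

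Power in a matched study comes from discordant pairs, whose number falls almost in proportion to exposure when exposure is rare. A fivefold drop in exposure therefore changes the answer materially. Section 9.5 is the full study-size section, and linaclotide is the exposure of main interest. A reader who relies on 9.5.2 could take 94 or 168 confirmed sets as enough to detect OR 4 or OR 3 for linaclotide, and could read a null result from that many sets as evidence against effects of that size.

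**Working it through.** **Inputs.** Two-sided alpha 0.05 and 80% power (Tables 2 and 3); 1:1 pairs (Table 3); 20:1 with Fleiss continuity correction (Table 2); exposure 5% (9.5.1, 9.5.2), 1% (9.5.2, 4.8) and 4% (4.8, upper end).

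**Case-control formula.** Let p0 be exposure in controls, p1 = OR·p0 / (1 + (OR−1)·p0), P = OR/(1+OR), and π = p0(1−p1) + p1(1−p0) the proportion of discordant pairs. Then

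m = [1.960/2 + 0.842·√(P(1−P))]² / (P−0.5)², and N = m/π.

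- OR 4: P = 0.80, m = (0.980 + 0.337)²/0.09 = 19.26.
- OR 3: P = 0.75, m = (0.980 + 0.364)²/0.0625 = 28.92.

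**Reproducing Table 3.**

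| p0 | π, OR 4 | N, OR 4 | π, OR 3 | N, OR 3 |
|---|---|---|---|---|
| 5% | 0.2065 | 93.3 → 94 | 0.1727 | 167.4 → 168 |
| 4% | 0.1714 | 112.4 → 113 | 0.1422 | 203.3 → 204 |
| 1% | 0.0481 | 400.8 → 401 | 0.0388 | 744.9 → 745 |

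All six agree with the printed cells.

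**Power of the printed set counts.** With N fixed, z = [√(Nπ)·(P−0.5) − 0.980] / √(P(1−P)).

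- 94 sets, OR 4, 1%: Nπ = 4.52, z = −0.856, power 19.6%.
- 168 sets, OR 3, 1%: Nπ = 6.52, z = −0.789, power 21.5%.
- At 4%: Nπ = 16.11 and 23.89, z = 0.561 and 0.559, power 71% for both.

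The approximation is, if anything, generous at 1%: an exact two-sided test cannot reach 5% with fewer than six discordant pairs (2 × 0.5⁵ = 0.0625).

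The design allows up to four controls per case. The Dupont extension of this formula to 1:4 matching, with no exposure correlation within sets, gives 51.5% (94 sets, OR 4) and 48.8% (168 sets, OR 3) at 1%, and 93% and 92% at 4%.

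**Cohort formula.** With r unexposed per exposed, incidence pu in the unexposed, pe = OR·pu/(1+(OR−1)·pu), p̄ = (pe + r·pu)/(1+r) and d = pe − pu:

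n′ = [1.960·√((r+1)p̄(1−p̄)) + 0.842·√(r·pe(1−pe) + pu(1−pu))]² / (r·d²),

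n = (n′/4)·[1 + √(1 + 2(r+1)/(n′·r·d))]², total = (r+1)·n.

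For OR 1.5 and pu = 1%: pe = 0.01493, d = 0.00493. At r = 20, n′ = 3,857, n = 4,067, total 85,415 (printed 85,416). At r = 99, n′ = 3,682, n = 3,884, total 388,440.

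| OR, incidence | Printed (20:1) | 24:1 (4%) | 99:1 (1%) | Power of printed size at 1% | at 4% |
|---|---|---|---|---|---|
| 1.5, 1.0% | 85,416 | about 100,700 | 388,440 | 28% | 74% |
| 2, 1.0% | 25,022 | about 29,500 | 113,018 | 30% | 74% |
| 1.5, 0.5% | 169,442 | about 199,800 | 770,503 | 28% | 74% |
| 2, 0.5% | 49,501 | about 58,300 | 223,546 | 30% | 74% |

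The formula reproduces all four printed sizes to within two patients. Power is obtained by inverting the same continuity-corrected formula. At 1% exposure both OR 1.5 sizes exceed the 329,000 patients available; the OR 2 sizes do not. At 4% all four fit.

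**The case against.** The strongest reply is that the protocol already contains the right numbers. Section 4.8 sizes at 1% and quotes 401 and 745 pairs, and Table 3 prints the 1% row. Nothing plans to stop at 94 or 168 sets. With 11,800 potential cases, 745 pairs need 745/11,800 = 6.3% confirmed with usable data, and 401 need 3.4%. Section 4.8 makes the final number depend on validation. Table 2 is labelled for a generic risk factor at an explicit 5%, and laxatives, age and comorbidities are also exposures of interest. The study is declared descriptive, without an a priori hypothesis. Four controls per case soften the shortfall at 1%, and at 4% they remove it for both set counts.

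All of that stands, and it limits the point to section 9.5. It does not remove the contradiction within 9.5.2 or make its 80% statement true for linaclotide at 1%.

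Three stronger readings are tempting and are not supported.

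- A reader might infer that the study itself has only 20–38% power. The low figures belong to the printed set counts and cohort sizes, not to the expected yield. The upper end of that range comes from the OR 2 cohort sizes with the continuity correction left out, which is not the method behind Table 2. By the protocol's method, the full 329,000 at 1% exposure has about 74% power for OR 1.5 at 1% incidence, and for OR 2 over 99% at 1% incidence and about 91% at 0.5%.
- A reader might multiply the 0.05% and 0.08% SCD frequencies in 9.5.2 by 329,000, get 165 to 263 cases, and conclude that 745 pairs are out of reach. Those frequencies are conditional illustrations that match the set counts (94/200,000 = 0.047%, 168/200,000 = 0.084%); they are not forecasts of confirmed cases.
- A reader might convert 1% ever-use into a much lower current-use prevalence and a requirement of thousands of pairs. Current use at index date cannot exceed ever-use, so the direction is right. The protocol gives neither a current-use figure nor the mean follow-up needed to derive one, and the person-years it does give belong to the superseded forecast.

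**Conclusion.** The point holds as an inconsistency in the study-size text. Section 9.5.2 states 80% power for linaclotide with 94 and 168 sets on an exposure that the same section and 4.8 have abandoned. With 1:1 matching the true figures are about one in five at 1% exposure and 71% at 4%; with four controls per case at 1% they are about one in two. The cohort sizes in 9.5.1 are correct as labelled for a generic 5% factor, but if read as linaclotide sizes at 1% they are too small by a factor of about 4.5 (388,440/85,416).

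This rests on the protocol's own alpha, methods and exposure estimates. The 1% is the CPRD expectation and the lower end of the three-country range; 4% is the upper end. Whether the study reaches 745 confirmed pairs depends on validation, and nothing here shows that it will not.

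**What to change.** - **Section 9.5.2.** Delete the wording that presents 5% as the expected linaclotide exposure. Replace the 94 and 168 examples with the 1% row of Table 3 (401 pairs for OR 4, 745 for OR 3), and give the 4% row (113 and 204) as the favourable bound. State that these are 1:1 figures.
- **Section 9.5.1 and Table 2.** Keep the 5% table, labelled as generic. Add linaclotide-specific sizes at 99:1 and 24:1 by the same continuity-corrected method, and say that the OR 1.5 sizes at 1% exposure exceed the cohort available.
- **Section 4.8.** State that 401 and 745 refer to confirmed cases, so that 745 is about 6.3% of the 11,800 potential cases. Add that the 0.1% and 0.5% rows of Table 3 (7,252 and 1,468 pairs for OR 3) apply if current use at index date is rarer than ever-use.

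The cost is a text edit and one table recalculation, with a less favourable stated sensitivity. No additional patients or data are required.
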